1.0 Study Design and Methods

Study Design

To address the study objectives, a pilot randomized controlled trial will be conducted.

Study population:

Group 1: Veterans

A convenience sample of Veterans , who are screened and diagnosed with Parkinson's disease (PD) and mild cognitive impairment in the executive function domain will be enrolled. Targeted enrollment for the intervention is 45; they will be randomized to one of three groups: CCT+PRIIS (n=15), CCT+PRIIS control (n=15) or CCT control +PRIIS control (n=15).

Group 2: Knowledgeable Informants

We will also enroll knowledgeable informants/caregivers of the enrolled Veterans. Thus, we will be enrolling civilians (however it is possible that caregiver could be a Veteran and this is acceptable). The purpose for enrolling a caregiver is to obtain their perspective on functional changes related to cognitive impairment in the Veteran living with PD. To obtain their perspective, they will complete the PD-Cognitive Functional Rating Scale (PD-CFRS) at three different time points during the study. The planned activities for the caregiver are the following: consent, demographic form, PD-CFRS at three different time points. The consent form, demographic form and PD-CFRS will be completed at their first visit. We will mail them the form when their Veteran completes the RCT, we will mail them the form again one month later. A knowledgeable informant/caregiver is not required in order for the Veterans to enroll. Targeted enrollment is 45, however we anticipate having to enroll 60 civilians due to Veterans being withdrawn – and thus the associated civilian will need to be withdrawn.

Below we list the inclusion and exclusion criteria for both Veterans and Knowledgeable Informants.

Group 1: Veterans

In general, eligibility criteria target Veterans with idiopathic PD and not other forms of parkinsonism. Thus, only Veterans older than 50 with PD diagnosed according to UK Parkinson's Disease Society Brain Bank

Diagnostic Criteria will be eligible. PD medication can influence cognitive function, thus, only participants receiving stable medication (i.e., no changes in medication or dose for the past month) and who are expected to remain on stable medication for the duration of the RCT will be eligible.

Inclusion criteria for Veterans:

- Diagnosis of PD as determined by the UK Parkinson's Disease Society Brain Bank Diagnostic Criteria⁴⁶
- age 50 and older
- receiving stable medication for at least 4 months (i.e., no changes in medication and medication dose in the past month) and who are expected to remain on stable medication for the duration of the study
- Mild cognitive impairment as determined by the MDS Level 2 criteria.
- Speak and read English

Exclusion criteria for Veterans:

- Dementia
- Failure to demonstrate decision making capacity
- cholinesterase inhibitor medication
- History of deep brain stimulation surgery
- severe depression
- severe anxiety
- severe apathy

Group 2: Knowledgeable Informants

Inclusion criteria for Knowledgeable Informants:

- age 18 or older
- Speak and read English
- Interacts with the Veteran on a weekly basis

Exclusion criteria for Knowledgeable Informants:

- Pregnant

Women and minorities will be included in the study as long as they meet the inclusion/exclusion criteria. Participants will not be excluded from the study based on their gender or ethnic background.

Study Phases

Phase 1: Initial Screening and Recruitment

Veterans will be recruited from the Hines VA Hospital (VAH). Based on the VA Administrative data bases, from 2012 -2016, 1,022 Veterans with PD were seen for a clinical visit at Hines VAH. At least 25% of them are expected to be PD-MCI All research procedures will be carried out under IRB and RR&D approved protocols at Hines VAH.

In order to gain access to Veterans being treated at Hines VA, study personnel will obtain appropriate data access approvals including partial HIPAA waiver. Once approvals are secured, we will identify research candidates using the national inpatient and outpatient files available at VA Informatics and Computing Infrastructure (VINCI). We will request access to data files on the Corporate Data Warehouse (CDW) (CDW Production Domains and Vital Status Files (including BIRLS), and CAPRI/VistAWeb, with real SSN identifiers located in VINCI using the Data Access Request Tracker (DART) system. Once this access is approved, we will

then search the database for the past 10 years (FY09-FY18) for Veterans who have had at least 2 diagnoses of PD and who have had a clinical visit at Hines. Initial screening will occur by reviewing electronic medical records. Patients will be excluded if they have a PD-D diagnosis, severe depression, anxiety or apathy, Deep Brain Stimulation (DBS) or are taking cholinesterase inhibitor medication. Those deemed eligible will be recruited for study participation. We will send these likely eligible Veterans a recruitment letter in the mail that briefly describes the study as well as notifies them that the research team will be calling to ask if they would like to participate in the study. At least 2 weeks after potential participants were mailed an informational letter, they will be contacted via phone to determine interest and complete a phone screening. In the initial attempt to contact the Veteran, we will leave only three messages, with a minimum of 24 hours between messages, and preferably at different times of the day.

The telephone conversation includes:

1. a description of the study and the time commitment required to complete the study (i.e., participation will last for approximately 2 months, this includes 4 study site visits.).
2. A list of prescribed and over-the counter medications and the length of time the participant has been on each medication will also be collected.
3. Identification of a potential knowledgeable informant/caregiver will be discussed. We would ask the Veteran to identify a person and give them our research contact number.

[figure not shown]
If the Veteran appears to be eligible after the phone screen, we would mail a letter to the Veteran along with the consent forms and HIPAA for themselves and a knowledgeable informant to review.

Once eligibility is determined for the Veteran, based on the phone screen, then the research team will call the Veteran to let them know if they are eligible or not. If they are eligible, we would schedule a time for them to continue talking on the phone to answer questions and schedule an appointment to review the consent forms and then discuss questions or concerns.

When the potential knowledgeable informant calls the research team, we will provide a description of the study and the time commitment required to complete the study. We will review eligibility criteria. If the person is eligible, we will mail them a letter with the knowledgeable informant consent form and HIPAA for them to review.

As a second method of recruitment, the research team will work with the clinical managers at the Hines Neurology Clinic to determine Veterans with an upcoming neurology clinical appointment. We will access their VA medical records (i.e., chart reviews) to screen for eligibility. If eligible, these Veterans will also be sent the same recruitment letter and receive the same phone call as described above. We will also work with agreeing Neurologists at Hines VAH on a third method of recruitment. In this case, the doctors will inform their patients of the study and give them a recruitment flier following their routine clinical visit. As a fourth method, we will

Figure 1: Study Phases

screen medical records of Veterans in relevant clinics, such as Neurology, Geriatric clinic and rehab clinic, which will be accessed through CPRS.

Phase 2. Informed Consent and Screening Procedures

Informed Consent: Authorized clinical researchers will meet with the eligible Veteran in a private room to review the consent form and all research procedures, risks, confidentiality measures and study contact information. All participants will be able to make their own decisions regarding research participation. They will be encouraged to have a family member or friend in the room during the discussion of the study. The participant will not be openly encouraged to participate in the research or told that there is any expected benefit from the experimental interventions during participation. Potential research participants will have access to research staff to assist with any questions or concerns until understanding is achieved to the judgement of the individual asking the question – this mean that discussion of the study can continue with additional phone conversations or additional visits. If a participant refuses participation, no further contact will be made.

Before the consent is signed, the decision-making capacity tool will be administered. This tool asks the Veteran to explain, in general, what the purpose of the study is and what is expected, in general from the participant. If the Veteran fails to demonstrate an understanding, they will not be eligible for the study.

When the signed informed consent forms are completed, a note will be made in the Hines VA EMR, and the original consent will be kept in a locked cabinet in a locked research office behind swipe-access doors in [name] of Hines VA. Additionally, a copy will be provided to the participant.

During the same visit for informed consent, participants will be asked to complete additional screening and neuropsychological testing. Table 1 lists all standardized tests. Completion of consenting and screening is expected to take approximately 3 hours.

Phase 1 In Person-Screening

Screening for Depression: Participants will be screened with the Beck Depression Index-II. Those scoring between 29- 63 will be withdrawn from the study as this indicates severe depression.

Screening for Anxiety: Participants will be screened with the Beck Anxiety Scale. Those scoring 12 or greater will be withdrawn from the study as this indicates severe anxiety.

Screening for Apathy: Participants will be screened with the Starkstein Apathy Scale. Those scoring 14 or greater will be withdrawn from the study as this indicates severe apathy.

Screening for global cognitive function: First, participants will be screened with the MoCA (e.g., level 1 screening). Those scoring below 21 will be withdrawn from the study as this indicated dementia.

Phase 2 In-Person Screening

Screening for PD-MCI: The following tests for 5 cognitive domains will be used. Executive function: Trail making test, Action Fluency test, Wisconsin Card Sorting Test. Memory: Hopkins Verbal Learning Test-Revised, Brief Visuospatial Memory Test-Revised. Visuospatial: Judgment of Line Orientation, Hooper Visual Organization Test. Language: Similarities, Boston Naming Test. Attention/working memory: Letter number sequencing, Stroop color word test

Additional tests and questionnaires: Theories of Cognitive Abilities, Need for Cognition Scale, Memory for

Intentions Test and Modified Fatigue Impact Scale. A questionnaire will also be administered to obtain demographic information (age, gender, ethnicity, race, and education level), service-related information (active duty or reserves and period of service time, and Parkinson's disease-related history (year of diagnosis, number of years on Parkinson's medication and side of motor symptom onset), and current general computer use and use of commercially available cognitive training tools.

Table 1: Standardized Assessment Tools for In-Person Screening Visit		
Assessment Name	Construct measure	Time to complete (min)
Phase One of In-Person Screening		
Beck Depression Inventory-II	Depression	10
Montreal Cognitive Assessment	Global cognitive function	10
Beck Anxiety Inventory	Anxiety	10
Starkstein Apathy Scale	Apathy	5
		Total time: 35 minutes
Phase Two of In-Person Screening		
Letter number sequencing	Attention/working memory	5
Stroop color word test		10
Wisconsin Card Sorting Test	Executive function	15
Trail making test		5
Action Fluency Test		1
Hopkins Verbal Learning Test-Revised	Memory	10
Brief Visuospatial Memory Test-Revised		10
Judgment of Line Orientation short version	Visuospatial	10
Hooper Visual Organization Test		15
Similarities test	Language	10
Boston Naming Test Short form		5
Theories of Cognitive Abilities	Expectation of cognitive change	3
Need for Cognition Scale	Enjoyment of cognitively challenging tasks	5
The Memory for Intentions Test	Prospective memory	15
Modified Fatigue Impact Scale	Fatigue	5
		Total Time: 124 minutes

Table 2. Guidelines from the Movement Disorder Society Task Force on Defining & Assessing MCI¹⁰	
Assessment:	
Level 1	Allows for diagnosis of possible PD-MCI using either a test to assess global cognitive function (i.e., the MoCA) or a limited battery of neuropsychological tests. Based on MoCA total scores, 26 or higher indicates PD-N, 21-25 indicates PD-MCI and less than 21 indicates PD-D ^{41,42} .
Level 2	Allows for diagnosis and subtyping of PD-MCI using a full battery of neuropsychological tests which should include at least two tests in each of the five domains most affected in PD.
Definition of impairment: Using neuropsychological tests and appropriate normative data; impairment is defined as 1 standard deviation below normative mean in 2 tests in the same domain or any two tests in different domains.	

Phase 3: Baseline data collection

Repeated measures/study outcomes are included in a standardized battery of test that will be repeated at baseline, endpoint and follow-up. The battery is expected to take approximately 130 minutes to complete.

Tests administered during screening (e.g., the BDI-II, MoCA, BAI, and HVLT, Memory for Intentions Test, and Modified Fatigue Impact Scale) will not be replicated at baseline, but are included in Table 3 below to indicate it is a repeated measure.

Table 3: Repeated Measures Assessment Tools used in the RCT			
Assessment Name (Abbreviation)	Outcome	Construct measure	Time to complete (min)
NIH-EXAMINER components:	1° (composite score of 7 tests listed below)	Executive function	29 total
Dot counting	2°	Working Memory	7
1-back			5
2-back			5
Flanker	2°	Cognitive Control	5
Set Shifting			5
Letter	2°	Verbal Fluency	1
Category			1
Hopkins Verbal Learning Test-Revised (HVLT)	2°	Memory	10
Symbol Digit Modalities Test (SDMT)	2°	Processing speed	5
The Memory for Intentions Test (MIST)	2°	Prospective memory	15
Monetary-Choice Questionnaire	2°	impulsivity	10
Parkinson's Disease-Cognitive Functional Rating Scale (PD-CFRS)	2°	Real-life function	5
The Activity Measure for Post-Acute Care™ (AM-PAC™) –Applied Cognition questionnaire	2°	Real-life function	10
Timed instrumental activities of daily living (iADL)	2°	Real-life function	15
Beck Depression Inventory-II	2°	Depression	10
Beck Anxiety Inventory	2°	Anxiety	10
Starkstein Apathy Scale	2°	Apathy	5
Montreal Cognitive Assessment	2°	Global Cognition	10
Epworth Sleepiness Scale	2°	Sleepiness	5
Modified Fatigue Impact Scale	2°	Fatigue	5
			Total Time: 144 minutes

Phase 4: Intervention

Participants will be randomized to one of three groups: CCT+PRIIS (n=15), CCT+PRIIS control (n=15) or CCT control +PRIIS control (n=15) and issued a VA iPad to take home and complete the study intervention.

Participants and researchers who are administering and scoring outcome measures will be blinded to group assignment. Effectiveness of blinding will be evaluated by using data collected from mid-point and endpoint questionnaires that assess perception of training intervention⁶⁹. The PI will oversee the RCT and coordinate research procedures and thus will not be blinded to treatment assignments. [name], who will be blinded to group assignments, will coordinate sensitive aspects of the study that require blinding.

CCT training games are developed by Posit Science Corporation, San Francisco, CA, and are designed to train components of EF specifically affected in PD (Table 5). Participants will be asked to complete, at home, 4 sessions/week for 8 weeks. Each session will take 30min; totaling 16hr of CCT training. No dose effect is established for CCT, thus we looked to the literature^{24,28} and expertise of consultants at Posit Science for guidance on the dose, and determined that 16 hours may be sufficient to detect effects of training on cognition. Progress of the training will not be fixed; training modules will be continuously adaptive, following "staircase" procedures⁷⁰, assuring that success in training on ~75% of exercise trials. While this leads to a

different progression of training across participants, it provides a customized, challenging and internally rewarding training experience that should increase performance motivation and optimize learning⁷¹. CCT active control will include 9 entertaining online games that are played on the same platform as the CCT games (Fig 2). Veterans will be asked to complete, at home, 4 sessions/week for 8wk.

For PRIIS, participants will work with a study team member to determine patient-centered prospective memory tasks. Participants will collaboratively agree on problem areas/areas that they would like to manage better (i.e., remember when to take my medicine) formulated in the form of up to three personal rehabilitation goals using the Bangor Goal-Setting Interview (BGSI)⁷². They will rate their own performance on these goals at initial and follow-up assessments. Participants will be taught to form a 'When X, I will do Y', recite the statement aloud three times, and imaging themselves performing the task during the situation in accordance with the statement for 30 s. In addition to the three patient-centered goals, a common goal for all participants in each group will be completing weekly CCT/CCT active control assignments (e.g., on Monday, Wednesday, and Friday, when I eat lunch, I will complete my cognitive training games).

PRIIS active control will include verbal rehearsal. These participants will be instructed to recite their prospective memory task (complete weekly intervention assignments) at least three times a day and study them for 30 s. Everyone will be given a handout with strategy instructions as reference. Weekly calls will be made to participants to assess their progress with the prospective memory task of completing weekly intervention assignments. Barriers, facilitators, and resources will be noted and discussed.

The study team member designated as the cognitive coach will make weekly phone calls to the participant to assess compliance and help troubleshoot any difficulties with the assigned programs. During the call, the cognitive coach will help the participant assess their progress with the prospective memory task of completing weekly intervention assignments (and for PRIIS the other goals). Barriers, facilitators, and resources will be discussed.

At midpoint and endpoint (weeks 4 and 8 of the intervention), participant's perception of the training will be assessed, over the phone and by a study team member, with a short questionnaire that will include questions such as: Are the games enjoyable? Are the games challenging? Do you look forward to playing the games? Are you motivated to play the games? Do you think your cognition is improving because of the games? Answers will be rated on a Likert scale. All participants will be reassessed with the neuropsychological battery at endpoint and one month after endpoint. During the one month after endpoint, participants will not be contacted during the one month except to remind them of their appointment for the follow-up assessment.

Specific to the CCT intervention, several factors may contribute to non-compliance with program use. Several elements of flexibility will be incorporated in the treatment schedule to accommodate the challenges that Veterans with PD may encounter. First, the participant may require extra time to complete the program. Participants will be asked to engage in four 30-minute sessions per week for 8 weeks, which is 16 hours in total.

Training progress and compliance will be automatically uploaded to a secure HIPAA-compliant server at Posit Science, and will be monitored weekly by the study staff. If participants have completed less than 12 of the 16 hours of total training, then they will be allowed up to 4 additional weeks to complete the intervention. To ensure a time-bounded study commitment, after a total of 12 weeks such participants will perform their post-assessment (completion) visit regardless of the number of sessions completed. Second, we expect that not all participants will complete four sessions every week. To accommodate this, during the weekly phone calls to participants, the study team will work with them to generate a feasible training schedule if they are finding it difficult to meet requirements. Third, there may be some cases in which a participant may wish to stop or minimize the use of the program going forward, while remaining in the study. Potential reasons for this

decision might be a change in health issues, family/personal issues or lack of interest in the intervention. However, the participant may want to meet their personal commitment to the basic scientific research of the study. In such cases, after a study team discussion with co-investigators, the participant will be permitted to cease using the program and be scheduled for a post-assessment (endpoint) visit at the appropriate time relative to the baseline assessment. If the participant completed at least 12 hours of training within 12 weeks, then a 1-month follow-up assessment will be scheduled. Fourth, some Veterans may not be able to complete the proposed training regimen in one sitting (i.e., 30 minutes) due to fatigue. To accommodate this issue, participants may choose to break the time into shorter segments, which are more easily manageable.

We will define “completers” of the intervention as those who completed at least 80% of the sessions.

Phase 5: Endpoint

Endpoint Behavioral Assessments:

All participants will complete the assessments listed in Table 3 in a private room with trained research staff at Hines. A semi-structured interview will also be conducted by trained research staff. This interview will take approximately 30 minutes and discussion will focus around feasibility of participating in the study, perception of training for the 2 interventions, usefulness of the weekly cognitive coach calls, and guess at treatment group allocation. We will audiotape this part of the session. The option to consent to audiotaping is included in the veterans's consent form

Phase 6: Follow-up

Follow-up Behavioral Assessments:

One month after the last intervention session, all participants will complete the assessments listed in Table 3 in a private room with trained research staff at Hines.

Unblinding:

Participants will be unblinded after the last participant completes the study. A letter will be mailed to the Veterans.

Knowledgeable informants/caregivers

Knowledgeable informants/caregivers enrolled in the study will be administered the PD-CFRS. Data from the informant will be collected at baseline in person and, to reduce burden of data collection, end-point and follow-up surveys will be mailed to informants for completion. Filling out this form three times (along with an initial demographic form) are the only research procedures performed by the knowledgeable informants/caregivers.

COMPENSATION FOR PARTICIPATION IN RESEARCH ACTIVITIES

Veteran participants will be compensated \$120 for completing all research procedures in this study. Participants will receive \$30 after completing the 2-3 hour long diagnostic confirmation screen. Participants will receive \$30 after completing baseline neuropsychological assessments, \$30 after completing endpoint neuropsychological assessments and \$30 after completing follow-up neuropsychological assessments.

Payment Procedures if screening and/or assessments are completed Hines VA: they will be reimbursed \$30 direct deposit via electronic funds transfer (EFT).

Knowledgeable informants/caregivers will not receive compensation.

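### The recruitment call gives participation as about 2 months with 4 site visits, but the plan's own schedule takes about 3 months, and just under 4 with the permitted extension

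*Combined protocol and SAP*

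**What the plan says.** Section 1.0, Phase 1 (Initial Screening and Recruitment) lists what the recruitment call covers. Its first item is the time needed to complete the study: "participation will last for approximately 2 months, this includes 4 study site visits".

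The schedule itself is set out later in Section 1.0:

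- **Training (Phase 4).** "Participants will be asked to complete, at home, 4 sessions/week for 8 weeks".
- **Extension (Phase 4, repeated in Section 2.0).** For participants with less than 12 of the 16 training hours done, "then they will be allowed up to 4 additional weeks to complete the intervention". The limit is that "after a total of 12 weeks such participants will perform their post-assessment (completion) visit regardless of the number of sessions completed".
- **Reassessment (Phase 4).** "All participants will be reassessed with the neuropsychological battery at endpoint and one month after endpoint". Phase 6 places the follow-up visit on site at Hines, one month after the last intervention session.
- **Visits.** Consent and screening share one visit (Phase 2). Baseline, endpoint and follow-up are separate assessments. The compensation section pays for these four occasions.

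**The concern.** The call counts all four visits but gives a duration that ends before the fourth. The missing month is the follow-up period.

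This is operative text, because it is what prospective participants hear when they are first asked about the study. Veterans found through upcoming neurology appointments get the same call, so the figure reaches more than one recruitment route. The people being recruited have mild cognitive impairment, and before signing they must explain in general terms what the study expects of them. A correct time commitment is basic to that.

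The follow-up visit also matters to the analysis. In Section 5.0 the contrast for sustained effects compares endpoint with follow-up, so it depends wholly on that visit. With 15 participants per arm, each missed follow-up removes 1/15 = 6.7% of an arm. A Veteran who planned for 2 months could be less ready to return in the third or fourth.

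**Working it through.** **Inputs**

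- Stated duration: about 2 months, with 4 site visits (Section 1.0, Phase 1).
- Training: 8 weeks (Phase 4). Check: 4 sessions × 0.5 h × 8 weeks = 16 h, as the plan states.
- Latest endpoint visit under the extension: 8 + 4 = 12 weeks (Phase 4; Section 2.0).
- Follow-up: 1 month after endpoint (Phase 4), or after the last session (Phase 6). The two agree when the endpoint visit directly follows the last session, as assumed here.
- Number of visits: $120 total ÷ $30 each = 4 (compensation section).
- Conversion (mine): 365.25 / 12 / 7 = 4.348 weeks per month.

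**Step 1. What the stated figure matches.** 2 months = 2 × 4.348 = 8.7 weeks. Training alone is 8 / 4.348 = 1.84 months. The stated figure therefore fits the intervention period and nothing beyond it.

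**Step 2. Total duration = weeks to endpoint + 1 month**

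| Schedule | Weeks | Months | Ratio to 8.7 weeks |
|---|---|---|---|
| Standard | 8 + 4.348 = 12.3 | 12.348 / 4.348 = 2.8 | 12.348 / 8.696 = 1.42 |
| Full extension | 12 + 4.348 = 16.3 | 16.348 / 4.348 = 3.8 | 16.348 / 8.696 = 1.88 |

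**Step 3. Sensitivity to the length of the follow-up month.** With follow-up at exactly 4 weeks, the totals are 12.0 weeks (2.8 months) and 16.0 weeks (3.7 months). The conclusion does not change.

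**Step 4. The gap before training.** The plan gives no interval between screening, baseline and the start of training, so Step 2 sets it to zero. If that gap is assumed to be 1 to 4 weeks, the totals become 3.1 to 3.8 months (standard) and 4.0 to 4.7 months (extended).

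**Step 5. Can any participant finish four visits in about 2 months?** Phase 4 lets a participant stop the program early and schedules a follow-up if at least 12 hours were done within 12 weeks.

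- At the planned 2 hours per week, 12 hours is reached in week 6. A follow-up one month after that last session falls at 6 + 4.348 = 10.3 weeks (2.4 months), which is still beyond 2 months.
- Someone who stops with under 12 hours, attends endpoint at about 8 weeks and has no follow-up scheduled would finish in about 2 months. That participant makes three visits, not four.

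**The case against.** The best defence is that the figure does little harm. The call is first contact, not agreement. Consent forms are mailed afterwards, a further call answers questions, and staff review all procedures in person before anyone signs. The schedule is clear in Phases 4 to 6, and nothing in the sample size, randomization, endpoints or model uses the 2-month figure. This stands, and it limits the point to a correction of recruitment wording.

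It does not rescue the figure. Reading 2 months as training time only fails, because the same sentence includes four site visits and describes the time needed to complete the study. The word approximately does not stretch to a missing month.

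A reader might infer more than the documents support:

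- **That Veterans agree to the wrong period.** Agreement comes at the later consent step. The consent form is not among the documents, so its stated duration is unknown.
- **That medication stability is judged over 2 months.** The criterion asks that participants be "expected to remain on stable medication for the duration of the study" and does not define that span as 2 months. The medication item in the call collects current drugs and time already on them, and no text links the criterion to the quoted figure.
- **That the recruitment letter repeats the error.** The plan says only that the letter describes the study briefly.
- **That follow-up loss will rise.** The documents give no data on this.
- **That the true figure is 1.5 to 2 times the stated one.** Those ratios come from counting every month as four weeks (12/8 and 16/8). With calendar months they are 1.4 and 1.9.
- **That 4 months is typical.** The extension applies only to participants with under 12 hours completed.

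**Conclusion.** The phone description is wrong as written. Four site visits on the plan's own schedule take about 12 weeks, about 3 months, against the approximately 2 months stated. For participants who use all the extra weeks they take about 16 weeks, just under 4 months. The ratios are 1.4 and 1.9. These figures assume calendar months, an endpoint visit directly after training, and no gap before training starts. Any such gap makes the understatement larger.

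The finding concerns the accuracy of what is said at first contact. The analysis plan does not depend on it, and an effect on follow-up attendance is plausible but not shown. The correction should still be made, because the number is given to prospective participants and costs almost nothing to put right.

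**What to change.** In Section 1.0, Phase 1, change the call description to approximately 3 months, up to about 4 months if extra training weeks are used, with 4 site visits. Check that the recruitment letter and the consent form give the same duration, and correct them only if they do not.

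While making this change, reconcile two statements on who is followed up: Phases 4 and 6 say that all participants are reassessed one month later, but the Phase 4 text on stopping the program early makes follow-up conditional on 12 hours of training. The duration told to Veterans should match whichever statement the sponsor intends.

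The cost is a wording change with an IRB text update, and possibly a few more refusals at first contact. Such refusals would come from accurate information and are preferable to losses after randomization.
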